4.4 Blinding

Due to the nature of the intervention subjects, study assistants, and researchers will not be blinded. The data manager will be blinded. Emergency unblinding is not foreseen.

5 Methods: data collection, management, analysis

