2.2 Aims

The overall aim of this study is to measure the effects of Mepilex® Border Sacrum on the skin structure and function during mechanical loading compared to (1) no dressing, (2) ALLEVYN Life Sacrum and (3) Optifoam® Gentle Liquitrap Sacrum.

The following objectives are determined:

(1) To measure the changes of skin temperature, stratum corneum hydration, erythema and skin roughness, (2) to evaluate clinical signs of pain and erythema and (3) to determine IL-1alpha and total protein of the sacral skin before loading (baseline) and after three and a

half hours loading with or without application of a dressing (Mepilex® border, ALLEVYN Life Sacrum, Optifoam® Gentle Liquitrap Sacrum).

3. Methods: Participants, interventions, and outcomes

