3.4 Study procedures and interventions

Volunteers will come to the study centre for four visits. In between, there are at least 3 weeks to prevent possible carry over effects. Therefore, the entire duration of one subject will be at least 9 weeks. The duration of one study visit per subject is approximately 5 hours. After four visits, each volunteer will have received each intervention once (A, B, C and D, see Table 1).

Table 1. Experimental interventions for the sacral skin

Intervention	Dressing
A	None
B	Mepilex® Border Sacrum
C	ALLEVYN Life Sacrum
D	Optifoam® Gentle Sacrum

After giving informed consent, subjects will lie down in supine position on a standard hospital mattress for a maximum of 10 minutes. Then subjects will turn around into prone position. Two fields of equal size (each 2cm x 2.5cm) will be marked with a skin pen, one for the baseline and one for the follow-up measurements. If an erythema has occurred at the sacral area during the 10 minutes in supine position, the investigational site will be marked within the reddened skin area. In case of no erythema, the test area will be identified by feeling the most protuberant point at sacrum. After marking the measurement area the subjects will acclimatize under standardized room temperature and humidity conditions (22±2°C, 40 to 60% rel. humidity) for 30 minutes with having the sacral skin uncovered. Subjects may lay (on the side) or sit during this period but must make sure that the investigational area is uncovered. After that, subjects will move into prone position and the following baseline measurements will be conducted according to CRC standard operating procedures (SOPs):

- (1) Measurement of skin surface temperature
- (2) Measurement of SC hydration (SCH)
- (3) Measurement of Erythema index (EI)
- (4) Visioscan images to measure Rz, Ra
- (5) Cyanoacrylate skin surface stripping (CSSS), to determine IL-1alpha and total protein of the sacral skin.

In addition to the instrumental measurements, erythema and pain will be evaluated clinically.

The measures of skin surface temperature, SCH and EI will be performed three times per measuring round. Two duplicate Visioscan images will be taken. CSSS will be performed at the end.

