After the baseline measurements a randomization envelope will be opened to allocate the subject to one of the intervention groups A, B, C or D (see Table 1). The dressings (B, C, D) will be applied or the skin will be left uncovered (A), followed by a 3.5 hours loading period. The subject will lie in supine position on a standard hospital mattress. Every 30 minutes the head of the bed will be elevated to 45° for five minutes. During these five minutes, the participants will be instructed to bend their knees and to drag the feet repeatedly forth and back 10 times. Then the head of bed will be moved back again and the subjects can relax. The whole exercise will be done six times, after 0.5, 1, 1.5, 2, 2.5 and 3 hours.

After 3.5 hours loading time in supine position the subjects will move into prone position. In case of interventions B, C or D the dressings will be removed. Then all skin measurements and CSSS will be conducted again. After the end of the measurements and procedures, subjects will leave the study site. They will come back for another three times completing the remaining interventions.

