3.6 Variables and outcomes

Due to the explorative nature of this study, no distinction between primary, secondary or other variables is made (Table 3).

Table 3. Variables and outcomes

Name	Method and metric
Skin phototype	
 • Classification according to Fitzpatrick (nominal)
Height	
 • Measurements in the CRC • m (metric)
Weight	
 • Measurements in the CRC • kg (metric)
Age	
 • Checking by looking at the ID card • metric
Sacral pain	
 • Subjects' self-report • Pain (yes/no) (nominal) • Time to pain reporting in minutes (metric)
Erythema	
 • Visual inspection • VAS (metric)
Skin surface temperature	
 • Skin thermometer based in infrared technique (Courage and Khazaka Electronic GmbH) • °C (metric)
SCH	
 • Noninvasive instrumental measure using the Corneometer CM 825 (Courage and Khazaka Electronic GmbH) • Arbitrary units, A.U. (metric)
EI	
 • Noninvasive instrumental measure using the Mexameter MX18 (Courage and Khazaka Electronic GmbH) • Arbitrary units, A.U. (metric)
Rz, Ra, Rmax	
 • Visioscan VC 98 (Courage and Khazaka Electronic GmbH) • µm (metric)
Cytokines	
 • Cyanoacrylate skin surface stripping (CSSS) (or another sampling method) • IL-1, total protein in pg/µg • ELISA

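### The reason given for not blinding subjects covers dressing versus no dressing, but not disclosure of which of the three dressings a woman is wearing

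*Combined protocol and SAP*

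**What the plan says.** Section 4.4 treats everyone at the bedside alike: "Due to the nature of the intervention subjects, study assistants, and researchers will not be blinded". The only masked role is stated next: "The data manager will be blinded".

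Section 2.2 sets one overall aim, which is to measure the effects of Mepilex Border Sacrum "compared to (1) no dressing, (2) ALLEVYN Life Sacrum and (3) Optifoam® Gentle Liquitrap Sacrum". Objective 2 in the same section includes pain.

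Section 3.4 gives the order of events at each visit. Before loading, "subjects will move into prone position and the following baseline measurements will be conducted". An envelope is then opened, and "The dressings (B, C, D) will be applied or the skin will be left uncovered (A), followed by a 3.5 hours loading period". Later, "After 3.5 hours loading time in supine position the subjects will move into prone position", and any dressing is taken off before the measurements are repeated.

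Table 3 in section 3.6 lists sacral pain as the subject's own report, recorded as "Pain (yes/no) (nominal") and as minutes until pain is reported. The section ranks no outcome above another.

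**The concern.** One reason is used for two different situations. Whether a dressing is present cannot be hidden from the wearer. Which of three sacral dressings is present is another question, and the plan gives no reason why the subject must know the answer. It also describes no step to withhold the product from her.

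Pain is the outcome exposed to this, because the subject is the measuring instrument. If she knows which product she is wearing, her expectations of it may affect whether she reports pain and how soon. Two of the three comparators in the overall aim are competing products. Section 2.1 says that high-quality head-to-head trials of the main products are lacking, so readers will look at these comparisons. Section 6.2 also has pain documented as an adverse event, so the same influence could reach the harms comparison.

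**Working it through.** The plan states no figure on this point, so the check sets the relevant sections side by side.

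**1. Does the procedure require the subject to know the product?** Section 3.4 has her prone for baseline, then has the dressing applied, then has her supine for 3.5 hours, then prone again before removal. No step depends on her seeing the dressing or hearing its name. Hypersensitivity to the study product is an exclusion criterion in section 3.3 and is settled at entry, so eligibility does not depend on disclosure at each visit. One limit applies: her position at application is not stated. That she is prone then is inferred from the prone baseline just before it. Only removal is placed explicitly after the move to prone.

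**2. When is pain reported?** Time to pain is recorded in minutes. It is therefore presumably reported mainly during loading, when the dressing is beneath her and out of sight. Concealment would be in force when it is needed.

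**3. Which comparisons can be protected?**

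| Comparison with Mepilex (B) | Can the subject tell the conditions apart without being told? | Does the reason in section 4.4 apply? |
|---|---|---|
| No dressing (A) | Yes, by feel | Yes |
| ALLEVYN Life (C) | Perhaps by feel; not readily by sight | Not by itself |
| Optifoam Gentle (D) | Perhaps by feel; not readily by sight | Not by itself |

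**4. Could she learn more than the current allocation?** Section 4.2 says that each envelope holds the randomized order, and section 4.3 has it opened after the first baseline measurement. An openly handled envelope could therefore show her the products for all later visits at visit 1. Because each woman wears all three dressings, she could then compare named products with one another.

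**5. Which outcomes are affected?** Temperature, hydration, erythema index, roughness, IL-1alpha and total protein are read by instrument or assay, and a subject's knowledge of the product is unlikely to move them. Visual erythema scoring is done by staff, so it concerns assessor masking, which is a separate matter. What remains is sacral pain.

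**6. How large is the effect?** The documents give no pain rates, no information on what subjects believe about the products, and no direction of expectation. A bias cannot be computed. The coarseness of the pain proportion can: with 12 women per intervention, one changed yes/no answer moves it by 1/12 = 8.3 percentage points. That holds for a change from any cause and is not an estimate of bias.

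**The case against.** The case against acting is substantial in several respects.

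- **Subjects may have no expectations.** They are healthy women aged 65 to 80, and nothing says that they know or prefer any brand. This stands: the mechanism is plausible but not shown. Company funding does not establish it either, since that bears more obviously on staff than on the woman reporting pain.
- **The plan does not say that she is told the product.** Section 4.4 says only that she is not blinded, which might mean merely that masking is not guaranteed. This stands as a reading of the text, but it leaves practice undefined and allows disclosure.
- **Masking will be imperfect.** Staff know the allocation throughout visits of about 5 hours. Section 2.1 ties dressing performance to material and structure, and each woman can compare the three by feel. A reader might infer that withholding the name makes the pain comparisons subject-blind and removes the bias. The documents do not support that: they do not describe how alike the dressings feel, and the staff could reveal the allocation.
- **The stakes are low.** The study is exploratory, section 5.2 is descriptive and plans no formal test between dressings, and pain shares one of three objectives with clinical erythema. This limits the weight of the point. It does not supply a reason for disclosure, and a descriptive analysis will not correct a reporting difference.

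A reader might also take the number of dressing visits, or the 8.3-point step, as the size of the problem. Neither measures bias.

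**Conclusion.** The point holds in a limited form. The reason in section 4.4 justifies leaving subjects unblinded to dressing versus no dressing. It does not by itself justify their knowing which of B, C or D is applied. Self-reported sacral pain in the two competitor comparisons is therefore open to expectation bias that could be reduced at little cost.

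The size and direction are unknown. The effect is confined to one unranked variable, recorded in two ways, and to pain entered as an adverse event. The comparison with no dressing cannot be protected by this route. The conclusion assumes that a sacral dressing is not readily visible to its wearer and that she is prone, or at least facing away, at application. It does not assume that the dressings feel the same. This is a worthwhile, inexpensive improvement; the trial's other outcomes do not depend on it.

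**What to change.** In section 4.4, limit the stated reason. Suggested wording: *Subjects are not blinded to dressing versus no dressing. They are not told or shown which of dressings B, C or D is applied at any visit, nor the remaining order.*

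In section 3.4, add that the envelope is opened, packs are handled, and dressings are applied, removed and discarded out of the subject's view and without naming the product.

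In the report, describe this as 'product not disclosed to subjects' and not as 'subject-blind'. State that staff were unblinded, that women may have felt a difference between dressings, and that the comparison with no dressing was open.

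The cost is a few sentences of protocol text and some discipline at the bedside, with no extra staff or visits. If the consent information describes open allocation, it may need a small change; the consent pages are not in the reviewed text, so this could not be checked. Under section 7.2, the ethics committee would be informed if this is made as an amendment. The remaining downside is that masking may be incomplete.

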5.1 Data collection and management

All study data will be recorded on paper source data and subsequently entered into an electronic database. After data are entered, a random subset will be verified by an independent person (source data verification) who was not involved in the data entry. All aspects of Data Management is managed by properly trained staff at Charité.

5.2 Statistical methods

Demographic characteristics will be described using numbers, proportions, means and standard deviations. Metric outcomes will be described using mean and spread parameters per intervention and time point. Baseline and follow-up parameters will be compared descriptively.

6 Methods: monitoring

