Recently, Mölnlycke Healthcare sponsored a study to investigate the effects of pressure ulcer preventive dressings on loaded and unloaded skin. Between July and October 2016 n = 8 healthy males (mean age 28 years) were included into an exploratory cross-over trial to explore the effects of Mepilex® Border Sacrum and Heel on the sacral and heel skin with and without loading (CRC-SP-A-26). Main results were that the dressings have an occlusive effect in terms of accumulation of heat and humidity, but this was not very different to loaded skin without dressings. This increase of stratum corneum and epidermal hydration softened the skin and contributed to changes of skin topography. Finally, results indicate that loading increased the inflammatory cytokine IL-1alpha and that this increase seemed to be slightly lower when a dressing was applied. This may indicate that the dressing may reduce the inflammatory response. The detailed results are reported in the full study report version 2, December 2016.

Overall, the study results indicate that cutaneous structure and function parameters can characterize the response of heel and sacral skin due to loading and that it is possible to measure a particular dressing effect. However, the sample size was small, the loading duration of 2.5 hours was short, shear forces were reduced to a minimum, and the sample was not representative for patients at PU risk. Therefore, there is a need to repeat this study using a more relevant target group such as aged females, to increase the mechanical loading in terms of pressure and shear, and to compare directly different dressing types.

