3.1 Study design

This study is an investigator initiated explorative randomized cross-over trial using intraindividual comparisons. In total four interventions will be compared at the sacral skin (Table 1).

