4.1 Assignment of interventions

After the baseline measurements are completed, opaque envelopes will be opened to assign the treatment order. In order to minimize bias, the product allocation will be randomized. A computerized simple 1:1:1:1 randomization scheme for four study visits will be applied for the sacral skin for $n = 12$ subjects. An example of a possible allocation is displayed in Table 4.

Table 4. Example for order of experimental interventions for the sacral skin

Subject number	Dressing application order visits 1, 2, 3, 4
1	C → A → D → B
2	B → D → C → A
3	A → C → D → B
4	D → A → B → C
5	B → A → C → D
6	A → C → B → D
7	B → C → A → D
8	...
9	...
10	...
11	...
12	C → B → D → A

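### Section 5.2 names no within-woman contrast between interventions, so the planned report would not show how precisely Mepilex is compared with no dressing, ALLEVYN or Optifoam

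*Combined protocol and SAP*

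**What the plan says.** Section 2.2 (Aims) sets out to "measure the effects of Mepilex® Border Sacrum on the skin structure and function during mechanical loading compared to (1) no dressing", and lists ALLEVYN Life Sacrum and Optifoam Gentle Liquitrap Sacrum as the second and third comparators. Section 2.1 gives as part of the rationale the need "to compare directly different dressing types". Section 3.1 describes an "explorative randomized cross-over trial using intraindividual comparisons", and section 3.4 confirms the pairing: "After four visits, each volunteer will have received each intervention once".

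Section 5.2 is the whole analysis plan. After a sentence on demographics it says "Metric outcomes will be described using mean and spread parameters per intervention and time point", and then "Baseline and follow-up parameters will be compared descriptively". The spread measure is not named.

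The study is declared exploratory in its title and in sections 3.1, 3.6 and 3.7. Section 3.6 adds that "no distinction between primary, secondary or other variables is made", and section 3.7 plans 12 women without a formal calculation.

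**The concern.** The comparison that section 5.2 names, baseline against follow-up, runs within an intervention. The comparisons in the aim run between interventions: B-A, B-C and B-D in the lettering of Table 1. No section says how these will be summarised or how the pairing will be used.

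Followed as written, the report would show eight cells (four interventions by two time points) for each outcome measured before and after loading. A reader could subtract one cell mean from another but could not say how well the difference is known. Using each woman as her own control is what the four visits are for, and the planned tables would not show what it gained.

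**Working it through.** The plan contains no precision or sample size figure to reproduce; section 3.7 says that none was calculated. The check is therefore whether the planned tables determine the precision of a contrast.

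**Inputs from the documents.** n = 12 (3.7); each woman receives all four interventions (3.4); summaries are marginal cell means and spreads (5.2).

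**Assumptions, not in the documents.** Complete data; a common SD σ in every cell; correlation ρ between values of the same woman at different visits; correlation r between baseline and post-loading values at the same visit.

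**Step 1: paired post-loading contrast.** The SD of the paired difference is σ√(2(1−ρ)). The 95% half-width is t(0.975, 11) × SD/√12, with t = 2.201, which is 0.635 × SD.

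| ρ | SD of paired difference | 95% half-width |
|---|---|---|
| 0 | 1.414σ | 0.90σ |
| 0.3 | 1.183σ | 0.75σ |
| 0.5 | 1.000σ | 0.64σ |
| 0.7 | 0.775σ | 0.49σ |
| 0.8 | 0.632σ | 0.40σ |

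The cell means and SDs are the same in every row. The ratio of the extremes is 0.899/0.402 = 2.2. For example, a cell-mean difference of 0.5σ has an interval of 0.5σ ± 0.635σ = −0.14σ to 1.14σ at ρ = 0.5, and 0.5σ ± 0.402σ = 0.10σ to 0.90σ at ρ = 0.8. The planned tables cannot tell these apart.

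**Step 2: what a reader could compute instead.** Treating two cells as independent groups gives t(0.975, 22) × σ√(2/12) = 2.074 × 0.408σ = 0.85σ, whatever ρ is. That is 0.847/0.635 = 1.33 times the paired half-width at ρ = 0.5, and 0.847/0.492 = 1.72 times at ρ = 0.7.

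**Step 3: which paired contrast to report.** The difference in change from baseline has SD σ√(4(1−r)), taking the correlation across visits as ρ for baseline and post-loading values alike. It beats the post-loading difference only if 4(1−r) < 2(1−ρ), that is, if r > (1+ρ)/2. The last column below is from simulation: 3000 trials per setting, with subject, intervention, visit and same-visit baseline as fixed terms. This uses 19 parameters for 48 values and leaves 29 df.

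| ρ, r | Post-loading difference | Change difference | Model |
|---|---|---|---|
| 0, 0.5 | 0.90σ | 0.90σ | 0.77σ |
| 0, 0.9 | 0.90σ | 0.40σ | 0.39σ |
| 0.3, 0.7 | 0.75σ | 0.70σ | 0.61σ |
| 0.5, 0.5 | 0.64σ | 0.90σ | 0.63σ |
| 0.5, 0.7 | 0.64σ | 0.70σ | 0.58σ |
| 0.5, 0.9 | 0.64σ | 0.40σ | 0.38σ |
| 0.7, 0.8 | 0.49σ | 0.57σ | 0.46σ |
| 0.8, 0.9 | 0.40σ | 0.40σ | 0.34σ |

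The model was narrower than the change score in all eight settings, by 3% (0.391/0.402) to 30% (0.631/0.899), with coverage of 0.943 to 0.956. All of this assumes equal variances. When the post-loading error SD was doubled under A only, at (0.5, 0.7), coverage fell to about 0.90 to 0.91 for B-A and rose to about 0.97 to 0.98 for B-C.

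**The case against.** The strongest reply is that this is a declared descriptive study. It has no primary variable, promises no confidence interval, and section 3.1 already commits it to comparisons within the individual; a three-sentence section 5.2 need not exclude them. Much of this stands. A reader might infer that the plan breaks a promise of inference, or that the crossover's pairing is lost. The documents support neither. No inference is promised, point contrasts can be read from the cell means if data are complete, and all study data enter a database (5.1), so the paired differences can be computed at any time.

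The exploratory label explains the lack of tests and of a powered sample size. It does not explain leaving out the comparison that defines the aim and the design. A paired difference with its spread is itself descriptive.

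Three further objections stand and shape the fix:
- A regression model cannot be presented as the required analysis, since its coverage fails if variances differ between interventions.
- The change score is not a safe default. At (0.5, 0.5) it is 42% wider than the model (0.899/0.631) and is also wider than the plain post-loading difference. Section 3.4 marks separate fields for baseline and follow-up, so r includes differences between fields and may be low.
- Pain (yes/no) and time to pain in Table 3 are not before/after metric outcomes and are not covered here.

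**Conclusion.** The point holds as a gap in the planned report that should be fixed. Section 5.2 does not carry the intraindividual comparisons of sections 2.2 and 3.1 into any contrast between interventions, and the tables it plans cannot show the precision of one. Confidence in the omission is high.

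The size is only illustrative. The half-widths of 0.90σ to 0.40σ rest on assumed correlations of 0 to 0.8, equal SDs and 12 complete women. A reader might take the 2.2-fold range as a loss measured for this trial, but the documents give neither ρ nor σ, and the ratio depends on the range chosen (0.635/0.402 = 1.6 from ρ = 0.5 to 0.8). The conduct of the study and the data collected are unaffected.

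**What to change.** Add to section 5.2:
- For each metric outcome measured before and after loading, report the within-woman differences B-A, B-C and B-D in the post-loading value as mean, SD and 95% CI from the paired differences (11 df with complete data).
- Label these exploratory, with no confirmatory tests.
- Keep the cell means as supporting tables, and name the spread.

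Two additions are optional. A model of the post-loading value with subject, intervention, visit and same-visit baseline can serve as a supporting analysis. It adjusts for visit, which is useful because section 4.1 says "A computerized simple 1:1:1:1 randomization scheme for four study visits will be applied", and simple randomization need not balance interventions over visits. Its assumption of equal residual variance should be stated. The difference in change from baseline can also be shown, on the understanding that it gains precision only if r exceeds (1+ρ)/2.

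The cost is a few sentences and a few lines of code on data the plan already collects, with no added women, visits or tests. The downside is the number of intervals. Seven outcomes (temperature, hydration, erythema index, Rz, Ra, erythema VAS, IL-1alpha/total protein), or eight with Rmax from Table 3, times three contrasts give 21 to 24 unadjusted intervals. If no intervention differed, 21 × 0.05 = 1.05 to 24 × 0.05 = 1.2 of them would be expected to exclude zero by chance. The report should say so beside the tables.
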